7.3. Deaths

If any subject dies during the study, a listing of deaths will be provided and all relevant information will be discussed in the subject narrative included in the CSR.

7.4. Clinical Laboratory Tests

Laboratory test results will be presented in standard international (SI) units. All laboratory data will be listed.

Summary statistics for chemistry, hematology, and urinalysis laboratory tests will be presented for screening, visits 2 and 3, and for the follow-up visit. Summary statistics for coagulation laboratory test will be presented for screening. Laboratory tests values and changes from baseline (absolute) to each visit and time point will be summarized using descriptive statistics.

All values will be compared with predefined criteria, as specified in [Table 1](#), to identify potentially clinically significant values or changes. These values will be listed in the subject data listings. The incidence of potentially clinically significant abnormal values will be summarized for laboratory variables using subject counts as specified in [Section 4.1](#).

Table 1: Criteria for Potentially Clinically Significant Laboratory Values

Test	Criterion value
Serum chemistry	
Alanine aminotransferase (ALT)	$\geq 3 \times$ ULN
Aspartate aminotransferase (AST)	$\geq 3 \times$ ULN
Alkaline phosphatase	$\geq 3 \times$ ULN
Gamma-glutamyl transpeptidase (GGT)	$\geq 3 \times$ ULN
Lactate dehydrogenase (LDH)	$\geq 3 \times$ ULN
Blood urea nitrogen (BUN)	≥ 10.71 mmol/L
Creatinine	≥ 177 μ mol/L
Uric acid Men	≥ 625 μ mol/L
Bilirubin (total)	≥ 34.2 μ mol/L
Hematology	
Hematocrit Men	< 0.37 L/L
Hemoglobin Men	≤ 115 g/L
White blood cell (WBC) counts	$\leq 3 \times 10^9$ /L, $\geq 20 \times 10^9$ /L
Eosinophils	$\geq 10\%$
Absolute neutrophil counts (ANC)	$\leq 1 \times 10^9$ /L
Platelet counts	$\leq 75 \times 10^9$ /L, $\geq 700 \times 10^9$ /L
Urinalysis	
Blood (HGB)	≥ 2 unit increase from baseline
Glucose	≥ 2 unit increase from baseline
Ketones	≥ 2 unit increase from baseline
Total protein	≥ 2 unit increase from baseline

ULN=upper limit of normal range

7.4.1. Laboratory Values Meeting Hy's Law Criteria

All occurrences of possible drug-induced liver injury that meet Hy's law criteria as defined in protocol Section 7.1.5.1 will be included in adverse events reporting.

7.4.2. Other Clinical Laboratory Tests

At screening, subjects will be tested for human immunodeficiency virus (HIV)-1, HIV-2, hepatitis B surface antigen, and hepatitis C antibody. These results will be presented in the subject data listings.

7.4.2.1. Urine Drug Screen

A urine drug screen will be performed at screening and on visits 2 and 3. The drug screen will detect the presence of amphetamines, cocaine, opiates, cannabis, barbiturates, and benzodiazepine. The urine drug screen results will be presented in the subject data listings.

7.4.2.2. Alcohol Screen

An alcohol breath analyzer test will be performed at screening and on visits 2 and 3. These results will be presented in the subject data listings.

7.4.2.3. Corticoid Plasma Levels

Endogenous corticoid plasma levels will be measured on visits 2 and 3 (immediately before the tracer injection). The analysis will include measurement of DHEA, progesterone, testosterone, cortisol, and, where feasible, androstanolone, allopregnanolone, pregnenolone. These results will be presented in the subject data listings.

7.5. Physical Examinations

Physical examinations, including height and weight (to be measured at the screening visit only), will be performed at screening, and at follow-up. An abbreviated physical examination will be performed on visits 2 and 3. Any physical examination finding that is judged by the investigator as a clinically significant change (worsening) compared with a baseline value will be considered an adverse event and reported as such.

Descriptive statistics for weight and height will be provided. Individual results will be presented in the subject data listings.

7.6. Vital Signs

Any vital sign that is judged by the investigator as clinically significant will be considered an adverse event and reported as such.

All individual vital signs results (pulse, systolic and diastolic BP, body temperature, and respiratory rate) will be listed.

Summary statistics for vital signs (pulse, systolic and diastolic BP, body temperature, and respiratory rate) in seated or supine position will be presented for screening, for visits 2 and 3, and for the follow-up visit. Vital signs values and changes from baseline to each visit and time point will be summarized using descriptive statistics. The incidence of potentially clinically

significant abnormal values will be summarized using subject counts and these values will be listed separately in the subject data listings.

Vital sign measurements will be present graphically for nominal measurements and change from baseline. Each graph will have measurement (e.g. systolic BP) per part of the study where y-axis is the measurement and x-axis is time. There will be a mean line with SD bars for each dose and each subject group (healthy subjects or HD patients).

Table 2 specifies the criteria for identifying vital signs as potentially clinically significant abnormal values. Note that in order to qualify as potentially clinically significant abnormal, a value needs to meet both criteria below: ie, have a value beyond the criterion value and a change of at least the magnitude specified in the change relative to baseline column.

Table 2: Criteria for Potentially Clinically Significant Vital Signs

Vital Sign	Criterion value	Change relative to baseline
Pulse	≥ 120 bpm	Increase of ≥ 15
	≤ 50 bpm	Decrease of ≥ 15
Systolic blood pressure	≥ 180 mm Hg	Increase of ≥ 20 mm Hg
	≤ 85 mm Hg	Decrease of ≥ 20 mm Hg
Diastolic blood pressure	≥ 105 mm Hg	Increase of ≥ 15 mm Hg
	≤ 40 mm Hg	Decrease of ≥ 15 mm Hg

7.7. **Electrocardiography**

Any ECG finding that is judged by the investigator as clinically significant (except at the screening visit) will be considered an adverse event and reported as such.

Summary statistics for ECG measurements will be presented for screening, days -1 and 1 of visit 2 and days -1, 1 and 2 of visit 3, and for the follow-up visit. ECG variables will be averaged in case of repeated measurements in a single visit. ECG variable results and changes from baseline (Visit 2) to each visit and time point will be summarized using descriptive statistics and also presented graphically.

ECG measurements will be present graphically for nominal measurements and change from baseline. Each graph will have measurement (i.e. QT) per part of the study where y-axis is the measurement and x-axis is time. There will be a mean line with SD bars for each dose and each subject group (healthy volunteers or HD patients).

Shifts in ECG findings (normal and abnormal as evaluated by the investigator) from baseline to each visit and time point will be summarized using subject counts. For overall, the worst postbaseline finding (the abnormal finding if there are both normal and abnormal findings) for the subject will be summarized.

7.8. Concomitant Medications or Therapies

All concomitant medications will be coded using the WHODD.

Use of concomitant medication or treatment will be monitored throughout the study.

The incidence of concomitant therapies and medications will be summarized using descriptive statistics by therapeutic class category and preferred term. Subjects are counted only once in each therapeutic class, and only once in each preferred term category. Concomitant therapies and medications will include all medications up to the end of study as defined in the study protocol.

A medication is classified as concomitant medication if one of the following conditions is met:

- If the medication start date and the medication stop date is missing
- If the medication start date is known and medication stop date is missing and medication start date is less than or equal to the study medication last date and flag for continuation is yes.
- If the medication start date is missing and the medication stop date is known and is greater than or equal to the study medication first date
- If the medication start date and the medication stop date are both known and the medication start date is less than or equal to the study medication last date and the medication stop date is greater than or equal to the study medication first date.

The prior and concomitant medication or treatment used by HD patients will be listed only.

8. TOLERABILITY VARIABLES AND ANALYSIS

Subject tolerability assessments (the number [%] of subjects who fail to complete the study, number [%] of subjects who fail to complete the study due to adverse events, and the number of subjects who experience treatment-emergent adverse events) will be summarized by part and cohort in the disposition table.

9. PHARMACOKINETIC ANALYSIS

9.1. General

The pharmacokinetic analysis set will be used for all pharmacokinetic analyses. No formal statistical analyses of the pharmacokinetic data will be performed. All data will be listed and summarized descriptively by part and cohort and presented in tabular and graphical form where appropriate.

9.2. Pharmacokinetic Parameters

The following pharmacokinetic parameters will be determined or calculated from the plasma concentration-time data using non-compartmental analysis for pridopidine and its metabolite TV-45065, when possible. Actual sampling times will be used in the analysis.

Table 3: Pharmacokinetic Parameters

Parameter	Description	SAS Programming Notes
C_{max}	Maximum plasma concentration. Observed peak analyte concentration obtained directly from the experimental data without interpolation, expressed in concentration units	CMAX from WinNonlin® (WNL)
t_{max}	Time to maximum plasma concentration. First observed time to reach peak analyte concentration obtained directly from the experimental data without interpolation, expressed in time units.	TMAX from WNL
AUC	All AUC values will be calculated using the linear up / log down method, expressed in units of concentration x time.	
AUC_{0-24}	Area under the plasma concentration-time curve from time 0 to 24 hours postdose.	AUC0_24 from WNL where partial time =24
AUC_{0-t}	Area under the plasma concentration-time curve (time 0 to time of last measurable analyte concentration).	AUCLAST from WNL
AUC_{0-inf}	Area under the plasma concentration-time curve (time 0 to infinity), calculated as: $AUC_{0-inf} = AUC_{0-t} + C_{tlast}/k_{el}$, where C_{tlast} is the last measurable analyte concentration.	AUCINF_obs from WNL
%AUC	Percentage of estimated part for the calculation of AUC_{0-inf} .	AUC_%Extrap_obs from WNL If $AUC_Extrap_obs > 20\%$ then associated parameters (AUC_{0-inf} , k_{el} , $t_{1/2}$) are flagged
$t_{1/2}$	Terminal elimination half-life, calculated as $\ln(2)/k_{el}$, expressed in time units.	HL_Lambda_z from WNL

Parameter	Description	SAS Programming Notes
V _d /F	Apparent volume of distribution of the drug following extravascular administration	Vz_F_obs from WNL

Additional pharmacokinetic parameters, including partial AUCs and respective average plasma concentration ($C_{average}$) to be inclusive of the PET scan duration, may be calculated as well, as deemed necessary.

9.3. Plasma Pharmacokinetic Analysis

9.3.1. Plasma Pharmacokinetic Concentrations

Plasma concentrations for pridopidine and its metabolite TV-45065 that are BQL of the assay will be substituted by half the lower limit of quantification (LLOQ) in the computation of mean concentration values. Missing values will be ignored when calculating mean concentrations. Descriptive statistics (n, mean, geometric mean, SD, CV, median, minimum, and maximum) will be used to summarize the plasma concentrations by part, cohort and nominal time point. If over half of the subjects at a given time point have values BQL then the descriptive statistics will not be presented and will instead display as BQL for the mean and missing for all other statistics (except the minimum and maximum value).

Linear and semi-logarithmic plots of the geometric mean plasma concentration by scheduled sampling time will be provided by part and cohort. These plots will show time in hours. The plots will match the summary table results and will not have an observation at a given time point if more than half of the subjects have values BQL.

Combined individual profiles of pridopidine and its metabolite TV-45065 in plasma by actual sampling time, showing all subjects in a single plot by part and cohort will be presented on both a linear and a semi-logarithmic scale (1 graph for each analyte and cohort).

Linear and semi-logarithmic plots of the individual plasma concentration of pridopidine and its metabolite TV-45065 by actual sampling time will be provided by subject. These plots will show time in hours. Individual plots will use the BQL handling procedure described below for “Pharmacokinetic Parameters”.

All individual subject plasma concentration data for pridopidine and its metabolite TV-45065 will be listed by part, cohort and nominal time point.

9.3.2. Plasma Pharmacokinetic Parameters

The pharmacokinetic parameters will be estimated from the pridopidine and its metabolite TV-45065 (where data permit) plasma concentration-time profiles for all subjects in the pharmacokinetic analysis set. The concentration data as provided by the Bioanalytical Laboratory and (derived) actual blood sampling times will be used in the pharmacokinetic calculations.

In estimating the pharmacokinetic parameters, BQL values at time 0, at a sampling time before the first quantifiable plasma drug concentration will be treated as zero. All other BQL values will

be treated as missing. Missing values will be ignored when calculating pharmacokinetic parameters.

Actual sampling times, rather than scheduled sampling times, will be used in all computations involving sampling times. If the actual time or dose time is missing, the scheduled time may be substituted in order to calculate the pharmacokinetic parameter.

The terminal elimination rate constant (k_{el}) will be determined by plotting the concentration data versus time on a semi-logarithmic scale. The time interval of the terminal elimination phase will be determined by visual inspection. Linear regression on log-transformed concentrations within this interval will be used to calculate the terminal elimination rate constant. At least 3 non-BQL data points are required to retain a reliable k_{el} and associated parameters. Points prior to and including C_{max} will not be included in this interval. If the adjusted r^2 from the regression is ≤ 0.80 and the residual area of the $AUC_{0-\infty}$ extrapolated is $>20\%$ then the associated pharmacokinetic parameters may be considered unreliable. The values will be included in the analysis, but will be flagged in the individual listing, accompanied by a footnote.

Descriptive statistics (n, mean, geometric mean, SD, CV, median, minimum, and maximum) will be used to summarize the calculated pharmacokinetic parameters by part and cohort. All individual pharmacokinetic parameters will be listed.

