2.4. Sample Size and Power Considerations

This PET study is exploratory in nature; therefore, no formal hypothesis testing is planned. Thus, based on clinical and practical considerations, a sample size of up to approximately 38 subjects (up to 4 subjects per dose level) is considered adequate for this type of study and to attain the study objectives. Up to 45 subjects are planned to be enrolled in this study to ensure up to 38 evaluable subjects. Adaptive study design will allow increasing or reducing the study total sample size or each dose/time cohort as necessary. This sample size may include up to 4 patients with HD, which may be added to study engagement of pridopidine to the D2R and to explore the effects of neurodegeneration.

It is anticipated that 3 dose levels will be sufficient to characterize the exposure-response profile. However, additional cohorts may be studied.

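### SAP Table 3 and SAP 9.3.2 flag terminal-phase PK parameters by different rules, a poor fit alone is never flagged, and flagged values stay in small-cohort summaries with no summary planned without them

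*SAP*

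**What the plan says.** Two places in the SAP set a reliability flag for parameters that depend on the terminal slope.

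- **SAP 9.2, Table 3 (%AUC row).** If the extrapolated share exceeds 20%, "then associated parameters" are flagged, and the row lists them as AUC0-inf, kel and t1/2. There is no condition on the fit. V_d/F has its own row in the table but is not in that list.
- **SAP 9.3.2.** Two conditions are joined by a conjunction: adjusted r² of 0.80 or less "and the residual area of the" AUC0-inf above 20%. If both hold, "then the associated pharmacokinetic parameters may be considered unreliable". The associated parameters are not named.

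On handling, 9.3.2 continues: "The values will be included in the analysis, but will be flagged in the individual listing", with a footnote. It then states: "Descriptive statistics (n, mean, geometric mean, SD, CV, median, minimum, and maximum) will be used to summarize the calculated pharmacokinetic parameters", by part and cohort. No summary without the flagged values is planned.

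On how kel is obtained, 9.3.2 says: "The time interval of the terminal elimination phase will be determined by visual inspection". It adds: "At least 3 non-BQL data points are required". Points up to and including Cmax are excluded from the fit.

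Protocol 6.1 and 9.6 cover the PK parameters but give no reliability rule, so the protocol does not settle which version applies.

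**The concern.** The two rules give different flags for the same profile, and neither uses goodness of fit in a way that changes anything. The terminal interval is chosen by eye and may rest on three points. An r² limit is therefore the main numerical check on a bad slope, and as written it does no work.

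Pharmacokinetics is a secondary objective (SAP 1.1.1), and a dose cohort has up to 4 subjects (SAP 2.1). At that size one half-life from a poor slope can set the reported mean and CV. The flag appears only in the individual listing, so a reader of the summary table would not see it. The stake is the credibility of the cohort summaries of t1/2, AUC0-inf and V_d/F.

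**Working it through.** The plan states no figure on this point, so there is none to reproduce. The documents give no pridopidine half-life either; all half-lives below are assumptions.

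**1. The two rules side by side**

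| Adjusted r² | Extrapolated | Table 3 | 9.3.2 |
|---|---|---|---|
| 0.95 | 10% | no flag | no flag |
| 0.95 | 25% | flag | no flag |
| 0.60 | 10% | no flag | no flag |
| 0.60 | 25% | flag | flag |

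The rules differ in the second row. In the third row a poor fit passes both. No row is flagged by 9.3.2 and missed by Table 3, so r² adds no flag for the three parameters that Table 3 names.

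**2. When extrapolation exceeds 20%**

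Sampling ends at 24 h (SAP 1.1.2.2). For a mono-exponential decline the extrapolated share is 2^(−24/t1/2). Setting this to 0.20 gives t1/2 = 24 × ln 2 / ln 5 = 10.3 h.

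| Assumed t1/2 (h) | Mono-exponential | One-compartment oral, assumed ka 1 or 2 per h |
|---|---|---|
| 6 | 6.2% | 6.6–7.1% |
| 8 | 12.5% | 13.1–13.7% |
| 10 | 18.9% | 19.6–20.4% |
| 12 | 25.0% | 25.7–26.5% |
| 16 | 35.4% | 36.1–37.0% |

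If true half-lives are near or above 10 h, the case where the rules differ (good fit, more than 20% extrapolated) would be common.

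**3. Leverage of one retained value in a cohort of 4**

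Assumed half-lives are 8, 10 and 12 h plus one aberrant value.

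| Fourth value | Mean (h) | Geometric mean (h) | Median (h) | CV |
|---|---|---|---|---|
| left out (n = 3) | 10.0 | 9.9 | 10 | 20% |
| 30 h | 15.0 | 13.0 | 11 | 67.5% |
| 50 h | 20.0 | 14.8 | 11 | 100% |
| 100 h | 32.5 | 17.6 | 11 | 139% |

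**4. How large an error can pass unflagged**

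Take a true 6 h mono-exponential profile with starting concentration 1 and a correct 24 h value, but a wrong fitted slope.

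- C24 = 2^(−4) = 0.0625. AUC0-24 = (1 − 0.0625)/(ln 2/6) = 8.115.
- Extrapolation is exactly 20% when C24/kel = 8.115/4 = 2.029. Then kel = 0.0625/2.029 = 0.0308 per h and t1/2 = ln 2/0.0308 = 22.5 h.
- A fitted half-life of up to 22.5 h, against a true 6 h, therefore passes both rules whatever its r².
- AUC0-inf becomes 8.115 × 1.25 = 10.14 against a true 1/(ln 2/6) = 8.66, a 17% excess.
- V_d/F varies as 1/(kel × AUC0-inf), so it is inflated by (22.5/6) × (8.66/10.14) = 3.2-fold.
- For a cohort of 6, 6, 6 and 22.5 h, the mean is 10.1 h, the SD 8.25 h, the CV 81%, the geometric mean 8.3 h and the median 6 h.

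The unflagged gap is therefore modest for AUC0-inf and large for t1/2 and V_d/F.

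**The case against.** **The rules can be reconciled.** SAP 9.3.2 says "if", not "only if", and its cases are a subset of those in Table 3. Flagging AUC0-inf, kel and t1/2 at more than 20% satisfies both texts. This stands: a reader might infer a flat contradiction that cannot be programmed, and the documents do not support that for these three parameters. A two-tier reading (Table 3 as listing flag, 9.3.2 as a narrower caution) is also possible, but both passages end in "flagged" and no separate marks are defined.

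**The plan does not declare the values unreliable.** A reader might infer that the SAP summarises numbers it has itself rejected. The text says only that they may be considered unreliable. This stands.

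**An obvious outlier would be caught.** For half-lives of 6, 6, 6 and a spurious 30 h the mean doubles to 12 h. But the 30 h value implies 57% extrapolated by 2^(−24/30), or 25% if only the slope of a true 6 h profile is wrong (2.71/(8.115 + 2.71)). Table 3 flags it either way, so that example shows the effect of retention, not the missing flag. The median stays at 6 h and the geometric mean is about 9 h. Individual values and profiles are also shown, so an aberrant value in a cohort of 4 is visible to anyone who reads the listings.

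**Excluding flagged values could be worse.** This stands. With 24 h sampling, exclusion above 20% removes subjects because their half-life is long, however good the fit, and biases t1/2 downward.

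**The consequence is limited.** "This PET study is exploratory in nature; therefore, no formal hypothesis testing is planned", and PK is summarised descriptively only (SAP 9.1). Cohort size may be increased (SAP 2.4), and same-dose data in one population may be pooled (SAP 4.1), which dilutes a single value. This limits the size of the point but does not remove it.

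**Conclusion.** The point holds as an inconsistency with a practical gap, and it should be fixed. The two flags differ for a well-fitted profile with more than 20% extrapolated. The r² criterion never adds a flag, a poor fit alone is never marked, and V_d/F is left to the unnamed associated parameters of 9.3.2. Retained values can raise the mean half-life of a cohort of 4 by 1.5-fold (one value of 30 h) to 3.25-fold (100 h) in the illustration. The geometric mean rises by about 1.3- to 1.8-fold, and the median barely moves.

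These sizes rest on assumed half-lives and mono-exponential decline, and on cohorts of 4 that are not pooled. How often such profiles would arise cannot be determined from the documents.

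A reader might infer that the primary occupancy result is at risk. It is not: the Emax model in Protocol 9.7 uses plasma concentration, not half-life. Cmax, tmax and AUC0-t do not depend on kel. AUC0-24 is likewise unaffected when the 24 h sample is quantifiable; the SAP does not say how it is completed otherwise.

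**What to change.** 1. State one rule in identical words in Table 3 and 9.3.2: flag if adjusted r² is 0.80 or less **or** extrapolation exceeds 20%.
2. Name the parameters it covers: kel, t1/2, AUC0-inf and V_d/F.
3. Present the descriptive summaries of these parameters twice, with and without flagged values, and give the n for each.
4. Do not simply exclude on extrapolation above 20%, for the reason given under the objection.

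The cost is SAP wording and one extra summary. Some of the summaries without flagged values will have a small n, and if half-lives are long a cohort could have none left; showing both versions makes that visible.
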